ESRD patients will be recruited at the Dialysis Units of the University of Connecticut Health Center, and the DCI Unit in Manchester, CT. The recruitment strategy includes study fliers posted in different locations including UCONN Health Nephrology and Dental Clinics and Dialysis Outpatient Units as well as DCI Unit in Manchester, CT. The PI has included [name] (UCONN Health and DCI Units) as a Co-Investigator in the study. All recruitment strategies and material will be approved by UCONN Institutional Review Board (IRB). Once UCONN Health IRB is approved, while DCI will follow a separate IRB process utilizing UCONN IRB approved consent forms.

Patient selection will be based upon administrative patient list review and/or study flyer. In case administrative list review is employed, medical record review will be performed by the dialysis unit director in each unit with the utilization of our screening form. The nephrologist/dialysis unit director will then review the proposed selection list based on clinical judgment and the pre-screening criteria. We have also developed recruitment tools (Pre-screening Form, study brochures), which are practical and easy to implement in order to assist the nephrologist and dialysis personnel during the pre-screening process. Once the pre-screening process is completed, the ESRD subjects will contact the study coordinator for screening appointment. After an explanation of the study, the overall risk/benefits analysis, written consent will be sought from each of the participants. Following consent, patients will receive a brief oral exam to establish eligibility based on the Screening Form. Dental sessions will be scheduled based on patient choice but preferably prior dialysis session to minimize patient fatigue.

Our team has an extensive experience with the dental management of ESRD patients. Our protocol has derived from a close collaboration between the dental and renal teams.

- Prior to entering the study and any oral intervention, ESRD patient with recent complete blood count is cleared by the nephrologist.
- Prior and during the dental procedures, vital signs are monitored as a standard of care in dialysis.

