- Since several drug metabolism and elimination takes place in the kidney, and for protocol adhesion, only analgesics such as acetaminophen and anti-inflammatory drugs such as aspirin will be prescribed and "realistically dosed", resulting to either a dose reduction or prolongation of the dosing interval. If any other anti-inflammatory medication is needed, the patient will be excluded from the study (as per exclusion criteria)
- There is no evidence-based recommendation on the use of prophylactic antibiotics in the dental management of ESRD patients due to the lack of data on the duration and effects of transient bacteremia post dental intervention. Our preliminary study, which was conducted without antibiotics, had in no adverse events to report. Transient bacteremia has been shown to resolve in less than 20min in systemically healthy individuals (Lockhart et al., 2008). Antibiotic overutilization and misuse result in selection of resistant microorganisms and reduced antibiotic efficacy. Therefore, in our study we plan to use antibiotics wisely only if recommended by the primary nephrologist for high-risk patients.

Methods

Study design and Subject selection: The proposed study will be a two parallel arm feasibility clinical trial that will recruit 72 ESRD subjects with periodontitis in a model of computerized block randomization, which will facilitate recruitment in each outpatient dialysis unit. Blocks will be determined as per 2x2x2 a priori categorization of age, race and gender. More specifically, the participants in 2 dialysis units (UCONN Dialysis/ DCI and DCI Manchester) will be randomly assigned to the study arms using a computer randomization program. As a result, once sequences are determined by the statistician, they will be concealed in opaque envelops and opened prior to the first recruitment in the unit. This study will include participants treated with dialysis 3 times a week. Out of 900 ESRD patients in recruitment sites, we estimated approximately 450 patients with periodontitis. Individuals will be included in the

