study if they are older than 21 years old; if they are ESRD on dialysis; if they have chronic periodontitis as defined before ⁶¹; if life expectancy is more than 1 year; if they have can provide consent form. Individuals will be excluded from the study if they had periodontal treatment within a year prior to the study initiation; if they have AIDS, or active malignancy; if they poorly adhere to dialysis protocol; in anticipation for kidney transplant during study period; if they are pregnant; if they have dementia; if they take anti-inflammatory medication, except aspirin≤325mg/d; if they use temporary catheter for dialysis access.

Population: This trial will recruit ESRD adult patients with periodontitis fulfilling the eligibility criteria below.

Inclusion criteria: Individuals will be included in the study if they are older than 21 years old; if they are ESRD on dialysis; if they have a minimum of 12 teeth; if they have chronic periodontitis as defined by the presence of at least two sites with CAL≥4mm or at least two sites with PD≥5mm not on the same tooth[26]; if they have no history of periodontal treatment within a year; if life expectancy is more than one year; or if they have can provide consent form.

Exclusion criteria: Individuals will be excluded from the study if they had periodontal treatment within a year prior to the study initiation; if they have HIV/AIDS, or active malignancy; if they poorly adhere to dialysis treatment; in anticipation for kidney transplant during study period; if they are pregnant; if they have dementia; if they take anti-inflammatory medication, except aspirin≤325mg/d; or if they use temporary catheter for dialysis access.

- > Subject characteristics and justifications:
 - Age: 21 years of age or older
 - Ethnicity: Please see NIH enrollment data in the grant application
 - Gender: Same as aboveVulnerable Population NA
 - Other characteristics (e.g. vulnerable populations; primary language etc.): NA

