1) Inflammatory Markers (Primary Outcomes) and Oxidative Stress Markers (Secondary outcomes): We aim to measure serum CRP (primary outcome) as a biomarker of inflammation as well as IL-6, F2 isofurans and F2 isoprostanes as markers of oxidative stress linked to atherosclerosis and poor CVD in ESRD²². A single serum CRP elevated measure has been shown to predict poor outcomes and sudden death in ESRD⁷⁵. Additional studies showed that IL-6 has been determined as a direct promoter of atherosclerosis and protein energy wasting through mechanisms of vascular calcification, muscle catabolism and cell aging ³² predicting poor outcomes in ESRD⁷⁵. In addition to testing the primary and secondary outcomes at baseline and 6-month, we will compare serial changes of the biomarkers throughout the study period at 2- and 4-month time points. Moreover, we will also measure F2 isoprostanes and isofurans, which are chemically stable, precise and easily detectable markers of lipid peroxidation⁷⁶ associated with poor outcomes in ESRD.²⁰

- *2) Patient-centered outcome (Secondary outcome):* Given the wide recognition of patient-centered outcome research by the Agency for Healthcare Research and Quality (AHRQ) and the NIH ⁷⁷, the validated OHIP-14 (true outcome) will evaluate patient's perception of oral status change ⁷⁸ and predictably assess periodontal treatment effect on oral health quality of life ^{79, 80}. Oral health perception has been determined fair to poor in groups of ESRD patients ⁸¹. The oral health related quality of life will be assessed with the OHIP-14 questionnaire ⁸². The response codes for the items in this tool are based on a five-point scale, ranging from "never" to "all the time".
- 3) Clinical Periodontal Parameters (Secondary Outcomes): The baseline full mouth periodontal examination will include missing teeth, probing depth (PD), bleeding on probing (BOP), clinical attachment loss (CAL), and plaque score (PS) at six sites on all teeth. BOP is an indicator of gingival (gum) inflammation and presence of active disease 83 . Periodontal parameters will be measured at baseline, at 2-, 4- and 6-months. Changes in probing depth (Δ PD) and BOP (Δ BOP) will be considered as the clinical outcome of treatment effectiveness and clinical response.

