- *4) Nutrition Biomarkers:* Serum albumin levels have been widely associated with malnutrition and mortality in ESRD ⁸⁴. We will use albumin levels less than 3.6g/dL as cutoff for malnutrition ^{85, 86}. As serum albumin has been associated with poor oral health status ([name] et a. 2013), we will assess changes in these biomarkers as a result oral intervention.
- 5) Adverse Event Frequency (Secondary outcome): For this outcome, pain, swelling, number of analgesics used (continuous) and presence of oral ulcers (dichotomous) will be recorded. More specifically, pain and swelling will be measured by ordinal scale (10cm horizontal Visual Analogue Scale, VAS).

Study Procedures and who will perform them:

Pre-screen Phase:

The nephrologist will review the potential subject's medical record to determine patient eligibility based on the criteria of the Nephrologist Pre-screen Form questions. The nephrologist will present the study to the potential subject and provide DCRC study contact information. If the potential subject is interested in participating, they will call the DCRC. At the time of the phone call from the pre-screened potential subject, the DCRC study staff will read the telephone script and collect name and scheduled dialysis treatment dates and times in order to schedule visit 1.

Visit 1: ESRD subjects will be consented in the dialysis outpatient units. Following the consent, the medical history will be reviewed and vital signs will be tested. During the screening process, brief periodontal examination will be performed to clear the periodontal inclusion criteria.

Visit 2 (Baseline): Full mouth periodontal examination will include: numbers of missing teeth, pocket depth (PD), clinical attachment level (CAL), plaque score (PS), bleeding on probing (BOP). In the same visit the OHIP-14 will be contacted in an interactive form to the both arms. Blood sample (6.5ml) will be collected for baseline inflammatory, oxidative stress and nutritional markers for both arms.

Visits 3-4 (Day 0): Full mouth scaling/root planning (Deep cleaning below the gum line) under local anesthesia will be performed to remove etiologic factors of the disease in both arms in one or 2 appointments. At the end of the visit, both groups will receive oral hygiene instructions.

*After Visits 3-4 test and control arm visits numbers change.

Test arm: (see time table Test arm, pg.14)

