Visit 5; Test (1-month post-Day 0): Oral hygiene reinforcement and behavioral modification only for the Test arm.

Visit 6; Test (2-month post-Day 0): Full mouth periodontal examination including oral hygiene assessment will be performed. Both arms will receive the OHIP-14. Blood samples (6.5ml) will be collected for inflammatory, oxidative stress and nutritional markers for both arms. Only in the test arm, the subject will receive supportive periodontal treatment including supragingival debridement and mechanical instrumentation (tooth cleaning) and oral hygiene reinforcement. Any remaining pockets will be treated with limited deep cleaning with local anesthesia. The control arm will receive no intervention. Visit 7; Test (3-month post-Day 0): Oral hygiene reinforcement and behavioral modification only for the Test arm.

Visit 8; Test (4-month interval post-Day o): Full mouth periodontal examination including oral hygiene assessment will be performed. Both arms will receive the OHIP-14. Blood samples (6.5ml) will be collected for inflammatory, oxidative stress and nutritional markers for both arms. Only in the test arm, the subject will receive supportive periodontal treatment including supragingival debridement and mechanical instrumentation (tooth cleaning) and oral hygiene reinforcement. Any remaining pockets will be treated with limited deep cleaning with local anesthesia. The control arm will receive no intervention. Visit 9; Test (5-month post-Day o): Oral hygiene reinforcement and behavioral modification only for the Test arm.

Visit 10; Test (6-month post-Day 0): Full mouth periodontal examination including oral hygiene assessment will be performed. Both arms will receive the OHIP-14. Blood samples (6.5ml) will be collected for inflammatory, oxidative stress and nutritional markers for both arms. At the end of the study both arms will receive supportive periodontal treatment including supragingival debridement and mechanical instrumentation (tooth cleaning) and oral hygiene reinforcement. Any remaining pockets will be treated with limited deep cleaning with local anesthesia.

Control arm: (see time table control arm, pg. 15)

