Recruitment and Consent Procedures: Patient recruitment was initiated on November 7th, 2017 with expected enrollment completion in April 2019. The trial is currently recruiting patients at UCONN Dialysis/DCI and DCI Manchester. The recruitment strategy includes study fliers posted in different locations including UCONN Health Nephrology, Dental Clinics and Dialysis Outpatient Units. All recruitment strategies and material were approved by UCONN Institutional Review Board (IRB) and DCI ARO. Figure 2 represents study flow chart.

The initial patient selection is based upon administrative and medical record review by the nurse manager with the utilization of the study's pre-screening form. The nephrologist reviews the patient selection and, based on clinical judgment and the pre-screening criteria makes the recommendation. We have also developed recruitment tools (pre-screening forms, study brochures), which are practical and easy to implement in order to assist the nephrologist and dialysis personnel during the pre-screening process. Once the pre-screening process is completed and the patient agrees to be approached, the study coordinator meets with the ESRD patient to present the study, the overall risk/benefits analysis, written consent is sought from each of the participants. The consent process may be extended to more than one meeting given the patient's level of fatigue [37].

Randomization and Allocation: The study follows a block randomization scheme. Blocks will be determined as per 2X2X2 a priori categorization of age, race and gender. More specifically, the participants in two dialysis units (UCONN Dialysis/DCI and DCI Manchester) will be randomly assigned to the study arms using a computer randomization program supervised by the study's biostatistician. Once sequences are determined, they remained concealed in opaque envelopes and opened prior to enrollment in the unit by the study coordinator.

Examiner calibration: The calibrated dental hygienist practices under the supervision of the Principle Investigator (PI). Following the calibration process, there was an agreement within ± 1 mm of 96%. Blinding: At 6-month visit, the final assessment will be conducted by the PI, who will be blinded to the study arm.

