Statistical methods: All analyses will follow the intent-to-treat principle. Given an attrition of rate of approximately 30% in the dialysis population, missing data will likely be from different sources (e. g., failure to complete questionnaire, study dropout, death). We will, therefore, utilize the multiple imputation algorithms of the IBM SPSS Missing Values 22 software[39, 40] to impute missing data. Data will be screened as recommended[41]. Standard diagnostic procedures will examine whether multivariate outliers exist, as well test for deviations from normality and linearity among dependent measures. When continuous measures are skewed, linear transformation will be attempted in order to preserve the inherent power of the continuous metric[42]. Descriptive analysis for all four time points will be including continuous measures with means, medians and standard deviations. Given OHIP-14 responses are ordinal, we will calculate the responses based on the "simple count", score frequencies as used before[43] and analyzed with non-parametric methods. Spearman correlation analysis will be used to test associations between clinical parameters and patient's oral health perception. In order to assess the effect of the confounding factors on oral response, univariate model will correlate PD and CAL changes with the baseline parameters, demographic, socioeconomic status variables, as well as diabetic control, dialysis adequacy and vintage, vitamin D levels.

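### The rule excluding a patient who needs another anti-inflammatory drug most likely acts after randomisation, and nothing keeps that patient in follow-up

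*Protocol*

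**What the plan says.** Section 4 of the protocol, Study Design & Procedures, lists rules for the dental management of dialysis patients. One bullet limits prescribing to analgesics such as acetaminophen and anti-inflammatories such as aspirin, at adjusted doses. It ends: "If any other anti-inflammatory medication is needed, the patient will be excluded from the study (as per exclusion criteria".

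The related statements are:

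- **Entry criterion** (Exclusion criteria). Patients are not eligible "if they take anti-inflammatory medication", with low-dose aspirin excepted.
- **Pre-entry step** (same bullet list). "Prior to entering the study and any oral intervention, ESRD patient with recent complete blood count is cleared by the nephrologist".
- **Allocation** (Randomization and Allocation). Envelopes are "opened prior to enrollment in the unit by the study coordinator". The SPIRIT table puts allocation in the enrolment and baseline part, before the interventions.
- **First dental treatment** (Visits 3-4, Day 0; both arms). "Full mouth scaling/root planning (Deep cleaning below the gum line) under local anesthesia will be performed".
- **Later treatment** (test-arm visits at months 2 and 4). "Any remaining pockets will be treated with limited deep cleaning with local anesthesia. The control arm will receive no intervention".
- **Primary outcome** (Outcomes and Rationale). "We aim to measure serum CRP (primary outcome) as a biomarker of inflammation".
- **Analysis** (Statistical methods). "All analyses will follow the intent-to-treat principle". Missing data are to be multiply imputed. Questionnaire failure, dropout and death are given as examples of how they arise.

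**The concern.** If the rule acts during the study, it takes randomised patients out because of an event that occurs after randomisation. The protocol does not say that sampling then stops. Equally, it does not say that an excluded patient continues with the 2-, 4- and 6-month blood draws, so those draws would probably not happen.

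Two features make such a loss awkward. Needing an anti-inflammatory drug is plausibly related to inflammation, and so to CRP itself. It may also be related to arm, because only the test arm is instrumented at months 2 and 4. Standard multiple imputation assumes that the observed data explain the missingness, which is doubtful here.

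This is a matter of conduct. A statistical analysis plan can define analysis sets and imputation models, but it cannot recover blood that was never drawn.

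**Working it through.** **When does the rule act?**

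- *Placement.* It follows directly on what the study team may prescribe. Prescribing limits apply to people already under study care.
- *Wording.* The entry criterion concerns patients who take such drugs. This sentence concerns patients for whom one is needed. Read as screening only, it would largely repeat the criterion.
- *Timing.* Allocation belongs to enrolment and baseline, and dental treatment starts on Day 0. A need arising from that treatment arises after allocation.
- *Against.* The parenthesis points back to the eligibility list, and the same bullets include a pre-entry clearance step.

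The on-study reading is the likelier one, but the text is ambiguous.

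**How large could the bias be?** The protocol gives no removal rate, so there is no stated figure to reproduce. All rates and correlations below are assumptions.

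Suppose patients in the top fraction *p* of a trigger variable are removed, and the trigger has correlation ρ with 6-month log CRP. On complete cases the arm mean shifts by

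ρ × φ(z₁₋ₚ) / (1 − p) SD.

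For p = 0.10 the multiplier of ρ is 0.1755 / 0.90 = 0.195. For p = 0.03 it is 0.0680 / 0.97 = 0.070. The arm difference therefore shifts by 0.125ρ, which is 0.038 at ρ = 0.3 and 0.062 at ρ = 0.5.

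For imputation, a simulation with 2,000,000 patients per arm imputed 6-month CRP by regression on an earlier CRP, with correlation 0.5 or 0.7 between the two. The trigger was either equally correlated with the earlier CRP or linked to it only through 6-month CRP.

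| Removed, arm vs arm | Complete cases, ρ = 0.3 / 0.5 (SD) | After imputation, range (SD) |
|---|---|---|
| 1% vs 0% | 0.008 / 0.013 | 0.002 to 0.010 |
| 2% vs 0% | 0.015 / 0.025 | 0.005 to 0.019 |
| 5% vs 2% | 0.018 / 0.030 | 0.005 to 0.022 |
| 10% vs 3% | 0.038 / 0.062 | 0.012 to 0.048 |
| 10% vs 10% | 0 | not simulated |

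Of 36 patients per arm, 1% is 0.36 of a patient, 2% is 0.72, 3% is 1.08 and 10% is 3.6.

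**Yardsticks.** The Power Analysis paragraph assumes d = 0.67 with 28 per arm. The standard error of an arm difference is then √(2/28) = 0.27 SD. Every figure in the table is far below both.

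**Does the earlier experience fix the rate?** The protocol reports no adverse events in its preliminary study. If that is the 16-patient pilot described in the background, the one-sided 95% upper bound for 0/16 is 1 − 0.05^(1/16) = 17%. It does not rule out any rate in the table.

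**Power.** No power argument is made. Enrolment may rise to a ceiling of 90, which at 30% attrition leaves 45 × 0.70 = 31.5 per arm against the 28 calculated.

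**The case against.** The strongest reply has four parts.

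1. **The sentence may be only an eligibility rule.** It cites the exclusion criteria, and on that reading no randomised patient is lost. This is possible, and the conclusion is hedged for it. But an ambiguous rule can be applied differently in the two dialysis units, and clarifying it does no harm if screening was meant.

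2. **The analysis already copes.** Intent-to-treat is stated, multiple imputation is planned, the list of missing-data sources is open-ended, and the hierarchical model uses all time points. Nothing removes an excluded patient from the analysis set. This stands in part. It makes the problem a tension and not a flat contradiction, and it makes the imputation column more relevant than the complete-case one. Neither imputation nor the model supplies samples that were never drawn.

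3. **The bias is tiny and the link to arm is speculative.** Full-mouth scaling is given to both arms on Day 0, so most treatment-related removals could balance, and equal rates give zero bias. Untreated control patients might even need drugs more often. This stands: the size is small and the sign unknown.

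4. **The remedy has costs.** Retained patients contribute drug-affected CRP values. If the drug lowers log CRP by an assumed 0.25, 0.5 or 1.0 SD, then at 10% vs 3% use the arm difference moves by (0.10 − 0.03) × 0.25, 0.5 or 1.0 = 0.018, 0.035 or 0.070 SD, similar to the bias avoided. Under intent-to-treat, however, that movement belongs to the effect being estimated. The trial was also already recruiting under this version, so an amendment comes mid-trial and patients already removed cannot be recovered. That limits the benefit without removing it.

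**Conclusion.** The concern holds. On the likelier reading, the protocol makes the primary outcome go missing by rule, for a reason plausibly tied to its value, while promising intent-to-treat analysis.

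Under the assumed rates and correlations, the bias left after imputation runs from about 0.00 to 0.02 SD if 1 to 2% of one arm is removed, up to 0.01 to 0.05 SD at 10% vs 3%. It vanishes at equal rates, and its sign follows whichever arm loses more patients. It does not threaten the trial's conclusion.

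The recommendation rests on asymmetry. Values taken after the drug can be kept or set aside later, whereas samples not taken are lost for good. Removals should at least be visible, since the Data and Safety Monitoring Plan tracks dropouts and their reasons. Confidence is moderate because the sentence can be read two ways. This is a cheap improvement that should be made.

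**What to change.** Apply the anti-inflammatory exclusion at screening only. Replace the last sentence of the prescribing bullet with wording to this effect: *a randomised participant who later receives another anti-inflammatory drug remains in follow-up, has all scheduled blood samples and examinations, and is analysed in the assigned arm; the drug and its start date are recorded.* The prescribing limits stay as they are.

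Optionally, add a supportive sensitivity analysis that sets aside CRP and IL-6 values taken after the drug, noting that this reintroduces informative missingness.

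The cost is one protocol sentence, one data field and the amendment that carries them, plus some drug-affected CRP values in the primary analysis.
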